8.3.1.3. Additional Analyses of the Primary Endpoint

Logistic regression modeling based on an as observed analysis using the same logistic regression model as Sensitivity Analysis #3 will be used to compare each GB001 group with placebo for the following:

- Each individual component of the primary endpoint separately. An individual component will not be analyzed if < 5 total subjects meet the criterion in the ITT population.
- The AM PEF and FEV₁ components only, as they represent worsening of asthma related to lung function.
- The rescue medication, ACQ-5 score, and severe asthma exacerbation components only, as they represent worsening of asthma related to asthma control.

Lastly, the primary endpoint will be analyzed in a manner similar to the primary analysis, but for the timeframe of by the Follow-up Visit (Week 28) rather than by Week 24.

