8.3. Analysis Methods

8.3.1. Primary Efficacy Analyses

The primary endpoint is the proportion of subjects who experience worsening of asthma by Week 24 as defined by at least one of the following:

- On 2 consecutive days, AM PEF \leq 75% of mean AM PEF measured over the last 7 days of the Run-in
- $FEV_1 < 80\%$ of baseline (Visit 2)
- Increase in rescue medication use of ≥ 6 puffs/day on 2 consecutive days compared to mean use over the last 7 days of the Run-in
- Increase in ACQ-5 score of ≥ 0.5 compared to baseline (Visit 2)
- The occurrence of a severe asthma exacerbation (asthma attack) defined as deterioration of asthma that leads to the use of systemic corticosteroids for at least 3 days, hospitalization, or an Emergency Department visit

Logistic regression modeling will be used to compare each GB001 group with placebo. The model will include covariates for treatment group, ICS dose (medium or high) at randomization, region (North America, Eastern Europe, Western Europe), baseline pre-bronchodilator FEV₁, and baseline ACQ-5 score. If the full model does not converge, a model with treatment group, ICS dose at randomization, and region as covariates will be utilized. If this reduced model does not converge, a model with treatment group and ICS dose at randomization will be used. In the rare case that convergence issues remain, only treatment group will be included in the model.

The number and proportion of subjects meeting the primary endpoint and corresponding 95% Wilson (Score) CIs (Wilson, 1927) will be summarized by treatment group. ORs, corresponding asymptotic 95% CIs along with the absolute differences and corresponding 95% CIs, and p-values will be summarized for each GB001 group versus placebo. The 95% CIs for the absolute difference will be Newcombe continuity-corrected CIs (Newcombe, 1998). Percentage reductions and corresponding 95% CIs will also be summarized. Lastly, the number and proportion of subjects meeting each component of the primary endpoint, with observed worsening of asthma, and with an assigned status of asthma worsening will also be summarized by treatment group. Subjects can meet more than one component of the primary endpoint.

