8.3.1.1. Sensitivity Analyses

Table 3 provides an overview of the primary and sensitivity analyses of the primary endpoint.

Analysis	Description
Primary analysis	Logistic regression where subjects with missing values are assigned asthma worsening status by Week 24 based on discontinuation of study treatment /withdrawal from study reasons
Sensitivity analysis #1: Missing Status Imputed as Asthma Worsening	Logistic regression where subjects with missing values are considered to have asthma worsening by Week 24
Sensitivity analysis #2: Worse Case Imputation	Logistic regression where placebo subjects with missing values are considered to NOT have asthma worsening by Week 24 and GB001 subjects with missing values are considered to have asthma worsening by Week 24
Sensitivity analysis #3: As Observed Analysis	Logistic regression using only those subjects with an observed status for asthma worsening by Week 24
Sensitivity analysis #4: MI	Logistic regression using MI
Sensitivity analysis #5: Per Protocol Population	Logistic regression in per protocol population using the same approach as primary analysis

 Table 3:
 Summary of Primary and Sensitivity Analyses of the Primary Endpoint

MI = multiple imputation

Sensitivity analyses of the primary endpoint will be conducted to evaluate the robustness of treatment effect under different assumptions and imputation algorithms. Sensitivity analyses will utilize the same logistic regression model as the primary analysis.

In general, for all sensitivity analyses, the number and proportion of subjects meeting each component of the primary endpoint, with observed worsening of asthma, and with an assigned status of asthma worsening will be summarized. The exceptions are Sensitivity Analysis #3 where the number of subjects with an assigned status will not be presented given that the analysis is among subjects with an observed status, and Sensitivity Analysis #4 where the number for each component will not be presented as multiple imputation (MI) will be performed for the overall asthma worsening status (yes/no).

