8.4. Examination of Subgroups

Subgroup analyses of the primary and two secondary (ACQ-5 score and pre-bronchodilator FEV₁) efficacy endpoints will be performed for all of the subgroups specified below. In addition, subgroup analyses of the secondary efficacy endpoint of annualized rate of severe asthma exacerbations will also be performed for select subgroups as specified below. For any subgroup level that does not comprise $\geq 10\%$ of the ITT population, the analyses based on the models will not be performed. The subgroups of interest are described below.

Demographic and general baseline characteristic subgroups:

- Age (years; $< 65, \ge 65$)
- Sex (male, female)
- BMI (kg/m²; < 30, \geq 30)
- Baseline ICS dose ([per randomization and per actual value]; medium, high, including comparison of GB001 medium to Placebo high)
- Region (North America, Eastern Europe, Western Europe)
- Total number of exacerbations in the past 12 months (1, > 1)

Efficacy-related baseline characteristic subgroups:

- Pre-bronchodilator percent predicted FEV₁ at Screening (%; $< 60, \ge 60$)
- ACQ-5 score at Baseline ($< 1.5, \ge 1.5$)

Biomarker baseline characteristic subgroups:

- Blood eosinophils at Baseline (GI/L; < 0.20, ≥ 0.20; < 0.25, ≥ 0.25 [including for annualized rate of severe asthma exacerbations]; < 0.30, ≥ 0.30)
- FeNO at Baseline (ppb; < 25, ≥ 25 [including for annualized rate of severe asthma exacerbations]; < 30, ≥ 30; < 35, ≥ 35; < 50, ≥ 50)
- Blood eosinophils and FeNO at Baseline ([blood eosinophils < 0.25 GI/L and FeNO < 25 FeNO ppb] vs [blood eosinophils ≥ 0.25 GI/L and/or FeNO ≥ 25 ppb] {including for annualized rate of severe asthma exacerbations}; repeat for 0.25 vs 30, 0.25 vs 35, and 0.25 vs 50)
- Blood eosinophils and FeNO at Baseline ([blood eosinophils < 0.25 GI/L and FeNO < 25 FeNO ppb] vs [blood eosinophils < 0.25 GI/L and FeNO ≥ 25 ppb] vs [blood eosinophils ≥ 0.25 GI/L and FeNO < 25 ppb] vs [blood eosinophils ≥ 0.25 GI/L and FeNO < 25 ppb] vs [blood eosinophils ≥ 0.25 GI/L and FeNO < 25 ppb] vs [blood eosinophils ≥ 0.25 GI/L and FeNO > 25 ppb]; including for annualized rate of severe asthma exacerbations)
- IgE (IU/mL; normal [≤ 158], high [> 158])
- 25-Hydroxyvitamin D at Baseline $(ng/mL; \leq 20, > 20)$
- Chloride at Baseline (mmol/L; ≤ Quartile 1, > Quartile 1-≤ Quartile 2, > Quartile 3-≤ Quartile 3, > Quartile 3, where quartiles are based on the ITT population)

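### When an arm has no events on a component of the primary endpoint, the component model gives a degenerate odds ratio, and the SAP's covariate-dropping fallback cannot repair it

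*SAP*

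**What the plan says.** SAP 8.3.1.3 compares each GB001 dose with placebo on each component by "Logistic regression modeling based on an as observed analysis using the same logistic regression model as Sensitivity Analysis #3". The only condition for fitting is the floor: "An individual component will not be analyzed if < 5 total subjects meet the criterion in the ITT population". It is a total over four arms.

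The model is inherited. SAP 8.3.1.1 states: "Sensitivity analyses will utilize the same logistic regression model as the primary analysis". SAP 8.3.1 then gives the terms: "The model will include covariates for treatment group, ICS dose (medium or high) at randomization, region (North America, Eastern Europe, Western Europe". Two continuous terms complete the list, FEV₁ and ACQ-5, both measured at baseline. Odds ratios carry asymptotic 95% intervals. The test behind the p-value is not named.

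The remedy for non-convergence has three steps. The first takes out the two continuous terms, and the second also takes out region, which leaves treatment and ICS dose. The third is the end of the road: "In the rare case that convergence issues remain, only treatment group will be included in the model".

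The SAP gives no penalised, exact or profile-likelihood method for this model, and no rule for an arm without events. SAP 8.3.1 does report by-arm counts and proportions for each component, with a bar graph.

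**The concern.** The fallback treats failure to converge as a covariate problem. That is right for a sparse region or ICS cell. It is wrong when the empty cell is a treatment arm, because the treatment coefficient then has no finite maximum-likelihood estimate whatever else is in the model. The steps give up the adjustment and still return an unusable treatment estimate.

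The component analyses show which parts of a five-part composite drive the result. Events on placebo with none on a dose is an informative pattern. Under the stated rule it can appear as an odds ratio of 0.000 with an unbounded interval and, if the test is Wald, a p-value near 1.

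**Working it through.** **Inputs.** About 120 subjects per arm, composite rates 25% and 10.2%, dropout 8% (SAP 2.5); floor of 5 events (SAP 8.3.1.3); terms and fallback (SAP 8.3.1). Component rates are not in the documents.

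**The plan's own figure.** With 120 × 0.92 ≈ 110 per arm, OR = (0.102/0.898)/(0.25/0.75) = 0.341 and ln OR = −1.077. SE = √(1/27.5 + 1/82.5 + 1/11.22 + 1/98.78) = 0.384. Power = Φ(1.077/0.384 − 1.960) ≈ 80%, as stated. This figure is for the composite; none is given for components.

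**Model size at the floor.** Slopes: 3 treatment + 1 ICS + 2 region + FEV₁ + ACQ-5 = 8. Five events give 5/8 ≈ 0.6 events per slope.

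**Does the fallback help?** Assumed counts of 10/4/3/0 (placebo/20/40/60 mg, 120 each), with simulated covariates, were fitted by maximum likelihood at all four levels. For 60 mg vs placebo:

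| Model | OR | Wald p |
|---|---|---|
| Full | 4.5e-8 | 0.990 |
| Without FEV₁, ACQ-5 | 4.5e-8 | 0.991 |
| Treatment + ICS | 4.3e-8 | 0.991 |
| Treatment only | 4.3e-8 | 0.991 |

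These are after 16 iterations. Stopping sooner gives p of about 0.73 to 0.74 (8 iterations) or 0.95 (12), still uninformative. On the same counts Fisher p is 0.0016 and likelihood-ratio p is 0.00016.

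If placebo is the empty arm, the odds ratios run the other way: 0/2/2/1 gives values of about 1e7, with p about 0.995.

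**Chance of an empty arm, given k events in total.** With equal risk it is (4·3^k − 6·2^k + 4)/4^k. At the planned ratio, the shares are 25/55.6 = 0.450 for placebo and 10.2/55.6 = 0.183 for each dose, and inclusion-exclusion applies. For k = 5: 0.0505 + 3(0.3630) − 3(0.00665) − 3(0.1017) + 3(0.00021) + 0.0184 = 0.833.

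**Chance that a contrast is hidden.** Fisher p is 0.060 for 5/120 vs 0/120 and 0.029 for 6/120 vs 0/120, so placebo needs at least 6 events. Summing the multinomial probabilities, at the planned ratio, of all splits with at least 6 on placebo and none on some dose gives the last column.

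| Total events | Empty arm, equal risk | Empty arm, planned ratio | Contrast hidden, planned ratio |
|---|---|---|---|
| 5 | 77% | 83% | 0% |
| 10 | 22% | 37% | 17% |
| 15 | 5% | 14% | 13% |
| 20 | 1.3% | 5% | 5% |

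**Worked example (assumed counts), 8/120 vs 0/120.** The Wald p is about 0.99, Fisher p 0.007 and likelihood-ratio p 0.0007. With two groups, the Firth estimate amounts to adding 0.5 to each cell: OR = (0.5/120.5)/(8.5/112.5) = 0.055, with penalised-likelihood p = 0.003. At 110 per arm, closer to an as-observed analysis, Fisher p is again 0.007.

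**The case against.** The strongest reply is that little is at stake. These are additional analyses with no multiplicity control and no decision attached. The by-arm counts and bar graph would show 8 against 0 directly. SAP 8.3.1.3 also analyses two grouped sets of components, which hold more events, and SAP 1 allows supplementary analyses labelled post hoc. All of this stands and keeps the severity low. It does not make the stated rule work, and a method chosen after an empty arm has been seen would be post hoc.

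Four stronger readings are tempting, and the documents do not support them:

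- **The p-value must print near 1.** That needs a Wald test, which the SAP does not specify. With a likelihood-ratio test only the odds ratio and asymptotic interval are degenerate.
- **The 5-event floor itself hides strong effects.** The most extreme split there, 5 vs 0, has Fisher p = 0.060. The 83% counts any empty arm, including placebo.
- **The 8.4 subgroup analyses share the fault.** For a level under 10% "of the ITT population, the analyses based on the models will not be performed". Otherwise SAP 8.4 fits one model with a treatment-by-subgroup interaction. Its own fallback drops that interaction, which removes separation from an empty arm-by-subgroup cell at the cost of the subgroup estimates.
- **The primary analysis is exposed.** At planned rates about 120 × (0.25 + 3 × 0.102) ≈ 67 events are expected. The chance of an empty GB001 arm is about 3 × 0.898^110, or 2 in 100,000.

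**Conclusion.** The point holds for the component models in SAP 8.3.1.3 and is minor. An arm with no events leaves the treatment odds ratio and its asymptotic interval degenerate at every step of the fallback. That follows from the model and needs no assumption about rates.

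How often it would happen is not known. The conditional chances assume that a component splits between arms as the composite is planned to, at 25:10.2; under equal risk a hidden contrast is rare (at most about 1.5%). Without conditioning on the total, and assuming 110 per arm and a risk ratio of 10.2/25 = 0.408, the chance of a hidden contrast is 2% at a placebo component rate of 2%, 7% at 3%, 13% at 5% and 3% at 10%.

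**What to change.** In SAP 8.3.1.3 only, specify Firth penalised logistic regression with the same covariates, and profile penalised-likelihood intervals and p-values. Apply it to all component models, or at least whenever an arm has no events and before any covariate is dropped. Show the by-arm counts beside each estimate. A simpler alternative is a minimum number of events per arm, with descriptive reporting below it. Sections 8.3.1 and 8.4 need no change on this account.

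The cost is one SAP sentence and one model option. The downside is slight shrinkage of odds ratios when events are few; results with ample events barely move. The rule should be recorded before unblinding.

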8.3.2. Secondary Efficacy Analyses

The secondary efficacy endpoints are listed in Table 1 and will be analyzed as described below.

8.3.2.1. Change from Baseline to Week 24 Endpoints

Change from baseline to Week 24 in ACQ-5 score, pre-bronchodilator FEV₁, postbronchodilator FEV₁, and AM PEF will be analyzed as described below. The ACQ-5 is a five-item questionnaire which has been developed as a measure of the subject's asthma control that can be quickly and easily completed (Juniper E. F., 2005). The response options for each of these questions consists of a zero (no impairment/limitation) to 6 (total impairment/limitation) scale with the total score ranging from 0 to 30. ACQ-5 score is the average of the 5 non-missing items and will be calculated at each visit for each subject. The minimal clinically important difference (MCID) is 0.5 points.

For AM PEF, the baseline value is defined as the mean over the last 7 days of the Run-in including the value on Day 1 and Week 24 is defined as the mean over the last 7 days prior to Week 24 including the value on the day of the Week 24 visit. For the other endpoints, the baseline value is defined as the last non-missing value on or before the date of the first dose of study treatment.

If the number of subjects overall with a missing change from baseline value is < 5% for a particular endpoint:

- The primary analysis will be analysis of covariance (ANCOVA) without MI.
- As a sensitivity analysis, mixed-effects model with repeated measures (MMRM) without MI will also be performed.

If the number of subjects overall with a missing change from baseline value is \geq 5% for a particular endpoint:

- The primary analysis will be ANCOVA with MI.
- As sensitivity analyses, MMRM with MI, ANCOVA without MI, and MMRM without MI will also be performed.

Post-bronchodilator FEV_1 will not be analyzed using MMRM as it is collected at only one post-baseline timepoint.

Each secondary endpoint of change from baseline to Week 24 will be analyzed using ANCOVA models. For this analysis, the MI procedure analogous to that described in Section 8.3.1.1.4 will be performed if the number of subjects overall with a missing change from baseline value is \geq 5% with the following modifications for cts data: (1) intermittent missing values will be imputed using the Markov Chain Monte Carlo (MCMC) method (Schafer, 1997), and (2) monotone missing values will be imputed using a regression model. Covariate adjustment will be the same as for the primary endpoint for ACQ-5 score and pre-bronchodilator FEV₁. For postbronchodilator FEV₁ and AM PEF, the covariates used in the model will be the same as for the primary endpoint except that baseline pre-bronchodilator FEV₁ will be replaced with baseline post-bronchodilator FEV₁ or baseline AM PEF, depending on the endpoint of interest. ANCOVA without MI will be performed similarly as described above without the imputation of values.

Descriptive statistics for change from baseline to Week 24 along with the LS means, SEs, and corresponding 95% CIs for each treatment group will be presented. Differences in LS means, SEs, corresponding 95% CIs, and p-values for each GB001 group versus placebo will also be constructed from the ANCOVA models.

In addition, each secondary endpoint of change from baseline to Week 24 will be analyzed by MMRM except for change from baseline to Week 24 in post-bronchodilator FEV₁. MMRM will

be performed using a restricted maximum-likelihood (REML)-based approach and an unstructured covariance structure to model within-subject error. The MMRM model will include change from baseline values up to Week 24 as the response variable; the fixed, categorical effects of treatment group, ICS dose (medium or high) at randomization, region, visit, and treatment group by visit interaction; and the cts, fixed covariates of baseline value and baseline value by visit interaction.

Parameters will be estimated using REML with the Newton-Raphson algorithm. Treatment comparisons will be derived from the MMRM. Differences in LS mean changes from baseline, the corresponding 95% CIs, and p-values with Kenward-Roger adjustment (Kenward, 1997) will be provided for comparison for each GB001 group versus placebo. LS means will be reported along with SEs and corresponding 95% CIs, and differences between treatment groups reported with LS means, SEs, corresponding 95% CIs, and p-values.

If a given analysis fails to converge due to the complexity of model specification, the following will be considered to enable model convergence: 1) use of maximum likelihood estimation instead of REML; and/or 2) a compound symmetric or first-order autoregressive covariance structure will be utilized, based on the covariance structure converging to better fit as determined based on Akaike's information criterion (Akaike, 1973).

Actual values and change from baseline values for ACQ-5 score, pre-bronchodilator FEV₁, postbronchodilator FEV₁, and AM PEF will be summarized by visit. Differences in means, SEs, and corresponding 95% CIs constructed from analysis of variance (ANOVA) models adjusting for treatment group only will also be presented. In addition, figures of mean actual values and mean change from baseline values, including SE bars, for ACQ-5 score and pre-bronchodilator FEV₁ by visit will be provided. Lastly, bar graphs of the LS means and CIs for Week 24 for ACQ-5 score and pre-bronchodilator FEV₁ will be provided.

Lastly, a sensitivity analysis with a different method of handling pre-bronchodilator FEV₁ measurements confounded by systemic corticosteroid use will be performed. Pre-bronchodilator FEV₁ measurements collected from systemic corticosteroid start date to systemic corticosteroid end date + 14 days will be excluded in order to reduce the confounding effect of systemic corticosteroids. If the number of subjects overall with a missing change from baseline is < 5%, then only ANCOVA without MI will be performed. If the number of subjects overall with a missing change from baseline value is \geq 5%, ANCOVA with MI and MMRM with MI will be performed.

ACQ-5 score, pre-bronchodilator FEV₁, post- bronchodilator FEV₁, and AM PEF data will also be presented in by-subject data listings.

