8. EFFICACY EVALUATION

8.1. Overview of Efficacy Analysis Issues

8.1.1. Handling of Dropouts or Missing Data

A variety of methodological approaches will be applied for handling subjects with missing data; full details are provided in Section 8.3.

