8.3.1.1.4. Sensitivity Analysis #4: Multiple Imputation

If the number of subjects overall with a missing observed status for asthma worsening by Week 24 is \geq 5%, then the following MI approach will be conducted as a sensitivity analysis.

The dichotomous outcome of asthma worsening by Week 24 will be imputed for subjects who have withdrawn from study without having experienced asthma worsening using a MI approach assuming that these subjects with a missing dichotomous outcome would have similar outcomes to subjects who had an observed status of asthma worsening by Week 24. The dichotomous outcome will be imputed directly as opposed to imputing the individual components of the primary endpoint and then deriving the composite outcome.

The following steps will be performed:

- Intermittent missing values will first be imputed using the Fully Conditional Specification method, which is appropriate for non-monotonic missing data for binary data.
- The monotone missing values will then be multiply imputed using the monotone logistic regression imputation method (Allison, 2005). A monotone missing pattern is such that in the event that a variable is missing it is implied that all subsequent variables are also missing (i.e. once a subject withdraws from study, no additional data is expected for that subject).
- For each stage, MI will be performed within treatment group with covariate adjustment the same as the primary analysis of the primary endpoint and non-missing outcomes for asthma worsening. Should convergence issues occur due to small cell size for the categorical covariates at either stage, they will be removed from the model.
- The primary analysis of the primary endpoint as described in Section 8.3.1 will be performed for each complete, imputed dataset.
- Fifty imputations will be performed.
- Results of the logistic regression on the multiple imputed data sets will be combined to generate an overall estimate and associated variance using Rubin's rules (Rubin, 1987).

The imputed data logistic regression model-based estimates of the proportion of subjects with asthma worsening, ORs, corresponding 95% CIs, and p-values will be reported. Percentage reductions and corresponding 95% CIs will also be provided.

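### No planned analysis of the continuous secondary endpoints tests whether withdrawn subjects did worse than missing-at-random predicts, and the MMRM drops a baseline covariate that the ANCOVA uses

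*SAP*

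**What the plan says.** SAP 8.3.2.1 sets two branches for the change-from-baseline endpoints, according to the share of subjects with a missing value.

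- **At least 5% missing:** "The primary analysis will be ANCOVA with MI", followed by "As sensitivity analyses, MMRM with MI, ANCOVA without MI, and MMRM without MI will also be performed".
- **Below 5% missing:** ANCOVA without MI is primary, and "As a sensitivity analysis, mixed-effects model with repeated measures (MMRM) without MI will also be performed".
- **Post-bronchodilator FEV1** has one post-baseline time point and therefore no MMRM in either branch.

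The MI is modelled on SAP 8.3.1.1.4, which works within treatment group and supposes that "subjects with a missing dichotomous outcome would have similar outcomes to subjects who had an observed status of asthma worsening". For continuous data, "monotone missing values will be imputed using a regression model"; no shift or reference-arm step is added.

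On adjustment, the ANCOVA rule is "Covariate adjustment will be the same as for the primary endpoint for ACQ-5 score and pre-bronchodilator" FEV1, meaning treatment, ICS dose, region, baseline pre-bronchodilator FEV1 and baseline ACQ-5. For AM PEF and post-bronchodilator FEV1, the endpoint's own baseline takes the place of baseline pre-bronchodilator FEV1. The MMRM has treatment, ICS dose, region, visit, treatment by visit, and "the cts, fixed covariates of baseline value and baseline value by visit interaction".

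For the primary endpoint, SAP 8.3.1.1 adds an analysis counting all withdrawals without an event as worsening, and a worst-case analysis that does so for GB001 only.

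**The concern.** A set of sensitivity analyses for missing data should vary the assumption that the data cannot verify. Here that assumption is that a GB001 subject who leaves would, by Week 24, have looked like a comparable GB001 subject who stayed. A subject who leaves and stops treatment may instead lose the benefit. If so, the planned estimates are too favourable and none of them is built to show it.

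The SAP takes this possibility seriously for the binary endpoint, where withdrawal for lack of efficacy counts as worsening (SAP 8.3.1, Table 2). The same subject's missing ACQ-5 or FEV1 is imputed from others in the same arm.

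The covariate mismatch is a second, smaller matter. If the ANCOVA and MMRM results differ, the reader cannot tell how much comes from the handling of missing data and how much from the changed model.

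**Working it through.** **1. The plan's own figure.** The only design figure is the power for the primary endpoint (SAP 2.5): 25% versus 10.2%, 120 per arm, 8% dropout, two-sided 0.05. None is given for ACQ-5, FEV1 or PEF.

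- Odds ratio: (0.102/0.898)/(0.25/0.75) = 0.341, a 65.9% reduction, as stated.
- Evaluable per arm: 120 × 0.92 = 110.
- Standard error of the log odds ratio: √(1/27.5 + 1/82.5 + 1/11.22 + 1/98.78) = 0.384.
- Power: Φ(1.077/0.384 − 1.96) = 80.0%, as stated.

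The planned 8% exceeds the 5% trigger, so the four-analysis branch is the expected one if missing Week 24 values run at about the dropout rate.

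**2. What each analysis assumes.**

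| Analysis | Condition needed |
|---|---|
| ANCOVA with MI | MAR, within arm, given covariates and earlier visits |
| MMRM with MI | The same |
| MMRM without MI (REML) | MAR |
| ANCOVA without MI (complete case) | Stricter: missingness depends only on the model's covariates |

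The extra FEV1 analysis in 8.3.2.1 removes values around systemic corticosteroid use and then applies the same methods. The COVID-19 analyses in SAP 3.3 are conditional examples, and none imputes worse outcomes after withdrawal.

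**3. Baseline covariates side by side.**

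| Endpoint | ANCOVA | MMRM | Absent from MMRM |
|---|---|---|---|
| ACQ-5 | FEV1, ACQ-5 | ACQ-5 | FEV1 |
| Pre-bronchodilator FEV1 | FEV1, ACQ-5 | FEV1 | ACQ-5 |
| AM PEF | PEF, ACQ-5 | PEF | ACQ-5 |

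**4. Size under reversion to placebo.** Let D be the difference under MAR and p the share of GB001 subjects who withdraw. If those subjects have placebo-like Week 24 outcomes, the expected difference is D × (1 − p). At p = 0.08 this is 0.92 D, or 8% smaller. The documents give no D. For an assumed ACQ-5 effect of 0.2 to 0.3 points, the loss is 0.016 to 0.024 points, against the 0.5-point minimal clinically important difference in SAP 8.3.2.1.

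**5. Size under a general shift.** If GB001 withdrawals are worse than MAR predicts by δ, the difference shrinks by p × δ. Both δ and the 5% and 15% rows are assumptions.

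| p | δ = 0.25 | δ = 0.5 | δ = 1.0 |
|---|---|---|---|
| 5% | 0.0125 | 0.025 | 0.05 |
| 8% | 0.02 | 0.04 | 0.08 |
| 15% | 0.0375 | 0.075 | 0.15 |

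For FEV1 at 8%, δ of 100 or 200 mL moves the difference by 8 or 16 mL. With D near 0.2, an ACQ-5 δ of 0.5 or more means doing worse than placebo, so those columns are harsher than step 4.

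**6. Do the planned methods react?** A simulation used 120 per arm, 400 replicates, assumed ACQ-like values, an effect of −0.2 before withdrawal, and random monotone dropout with δ added after withdrawal in GB001 only.

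| Dropout, δ | Full data | Complete case | Within-arm MI | Likelihood |
|---|---|---|---|---|
| 8%, 0 | −0.194 | −0.197 | −0.197 | −0.197 |
| 8%, 0.5 | −0.163 | −0.203 | −0.203 | −0.203 |
| 8%, 1.0 | −0.126 | −0.205 | −0.207 | −0.208 |
| 15%, 1.0 | −0.046 | −0.196 | −0.197 | −0.197 |

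The likelihood column stands in for the MMRM. All three methods stay near −0.20 while the full-data difference moves, so their agreement gives no warning of this departure.

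**The case against.** The case for the plan has real strength, and most of it stands.

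- **The analyses are not bound to agree.** A reader might infer that agreement among the four is guaranteed and therefore empty. It is not. Complete-case ANCOVA discards withdrawn subjects' post-baseline visits, while MI and MMRM use them. In a second simulation (effect −0.30, 8% dropout per arm, dropout driven by poor interim response in GB001 only), complete case gave −0.365 and within-arm regression imputation −0.302, a gap of 0.063. With the same selection in both arms, or random dropout, the two agreed. The contrast can thus expose selective withdrawal that differs by arm. It cannot expose unseen outcomes that are worse than MAR predicts.
- **Disagreement can be interpreted within pairs.** A reader might infer that no disagreement could be traced to missing data. But ANCOVA with and without MI share covariates, and MMRM with and without MI share a model. Only the ANCOVA-versus-MMRM contrast is confounded. In a randomised linear model, omitting a baseline covariate mainly costs precision.
- **MMRM with MI is not a pure duplicate.** Its imputation model carries the second baseline covariate that MMRM without MI lacks. It still adds no new assumption, and aligning the covariates removes most of what distinguishes it.
- **SAP 8.1.1 is not contradicted.** It says "A variety of methodological approaches will be applied for handling subjects with missing data" and refers to all of Section 8.3, which includes the primary-endpoint checks. Those cover the composite, not the continuous changes.
- **Missing data are limited by design.** Protocol 4.1.1 and 7.1 encourage subjects who stop treatment to continue visits.

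**Conclusion.** The point holds in a limited form. Every planned analysis of ACQ-5, pre-bronchodilator FEV1, post-bronchodilator FEV1 and AM PEF assumes MAR or stricter, and none probes worse-than-MAR outcomes after withdrawal. The MMRM for the three repeated endpoints also leaves out one baseline covariate that the ANCOVA uses, which blurs one contrast and gives up some precision.

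The likely size is modest: 8% of the treatment difference at the planned 8% dropout. This assumes full reversion to placebo, a missing Week 24 value for every dropout, and the same MAR effect in those who leave. A reader might infer losses of 15% or more, but the documents give no dropout rate above 8%. SAP 3.3 foresees more withdrawals and missed visits from COVID-19 without a figure. These are secondary endpoints, so the gap does not threaten the primary analysis. It limits what can be claimed about the robustness of the secondary results.

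**What to change.** 1. **Align the MMRM.** Give each MMRM the baseline covariates of that endpoint's ANCOVA, each with its interaction with visit: baseline pre-bronchodilator FEV1 and baseline ACQ-5 for ACQ-5 and for pre-bronchodilator FEV1; baseline AM PEF and baseline ACQ-5 for AM PEF. This applies in both branches and is the only change needed below 5% missing.
2. **Add one analysis that departs from MAR.** When at least 5% of Week 24 values are missing, replace MMRM with MI in the 8.3.2.1 list by a named reference-based MI, for example jump-to-reference, followed by the same ANCOVA. Withdrawn GB001 subjects are then imputed from the placebo model after withdrawal; intermittent gaps are imputed as now. Add the same analysis for post-bronchodilator FEV1, which has no MMRM to replace.
3. **Update SAP Table 1** to match.

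The number of analyses is unchanged for the three repeated endpoints and rises by one for post-bronchodilator FEV1. Protocol 9.4.1.2 specifies only ANCOVA for these endpoints and need not change. The cost is minor programming and a sensitivity estimate that will usually be slightly less favourable. The change should precede the interim unblinding to which SAP Section 1 ties its finalisation; analyses added beyond the SAP must be labelled post hoc.
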